## STATISTICAL ANALYSIS PLAN

### Hypotheses

#### *Primary Outcomes*

The overall purpose of this study is to identify the impact of nutrient warnings on product selection and other outcomes compared to GDA labels, Nutriscore labels, and a no-label control, in Colombia. The primary objectives of this study are to evaluate our hypotheses that, compared to GDA, Nutriscore, and control, a nutrient warning label will lead to:

1. Lower selection of the less healthy product in a set of two products as the product the consumer most wants to buy.
2. Better ability to correctly identify which product of a set of two has higher levels of sugar.

We will also explore whether the impact of the nutrient warning (vs. other study conditions) on these two primary outcomes differ by respondent's educational level.

### *Secondary Outcomes*

We hypothesize that the nutrient warning label (compared to other label types) will:

1. Have higher perceived message effectiveness.
2. Be the most discouraging label.

We hypothesize that the nutrient warning label (compared to all other conditions) – and all conditions compared to the control – will:

1. Increase the ability to correctly identify the most unhealthy product when compared with two options.
2. Increase the ability to correctly identify whether a single product contains excess sugar, saturated fat, or sodium.
3. Lower intentions of purchasing a product high in the nutrient of concern in the next week if it were available.

### **Statistical Methods**

We will use complete case analysis to handle any missing data. We will descriptively report unadjusted means (and standard deviations) and percentages for the primary and secondary outcomes.

We will use a two-sided critical alpha of 0.05 to conduct all statistical tests.

### **Sensitivity Analyses**

For PME, we will take the average of the 3 items for each product type if  $\alpha > .70$ . For all outcomes assessed between-subjects only, we will then assess whether the outcomes vary by study arm with regression models (linear for continuous outcomes and logistic for dichotomous outcomes).

For outcomes with multiple measurements per-person, we will fit mixed effects linear regression models for continuous outcomes (including PME) and a mixed effects logistic regression model for binary outcomes (including product selection, label selection, identification of healthier products), treating the intercept as random to account for repeated measures.

We will include indicator variables for warning message (between-subjects) and product type (within-subjects), as well as an interaction of warning message and product type. We will use postestimation commands to conduct pairwise comparisons of the predicted means to examine differences by all label types. We will correct for multiple comparisons. To evaluate the most discouraging label, we examine the proportion of participants that selected each warning label as the most discouraging and will conduct z-

tests to explore statistical significance of these differences. To assess whether the effect of the warning label on the primary outcomes differs by education, we will test for an interaction of warning label with low versus high education level (specified as dummy variables) and use a Wald chunk test to determine the joint interaction. We will use postestimation commands to predict means by warning label and education level and conduct pairwise comparisons of the predicted means.

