Following online consent, Qualtrics will equally randomize participants to one of the four front-of-package label conditions: nutrient warning, Nutri-Score, GDA, or a no-label condition. On Qualtrics, participants will complete three tasks. They will be asked to complete a selection task, in which participants will be asked to select which fruit drink is higher in sugar, which they would rather buy, and which is most unhealthy. The fruit drinks will be displayed with the labels corresponding to the participant's randomly assigned label condition. We will only include selection tasks for one type of product due to survey space constraints. Following the selection tasks, the participant will be asked to complete a single product assessment task. They will view a prompt that reads: "The next questions are about food products. You will look at a few different products and answer questions about each one. Please keep in mind that this study seeks to evaluate your survey responses and not the sale of the product." Then, they will answer a series of questions about the yogurt, cookies, and sliced bread, which will show the participant's randomly assigned label condition. The participants will answer all questions about one product at a time (displayed in random order). After these, the participants will answer objective understanding and PME questions about the breakfast cereal. The breakfast cereal is always displayed last as the nutrient warning condition contains two labels. Finally, the participants will be randomly assigned to see the yogurt, cookies, or sliced bread again (one product only). However, this time, the product will not fashion a label. Instead, the three label types (nutrient warnings, GDA, and Nutri-Score) will be displayed underneath the product and the participant will be asked to select the most discouraging label. The study will end with standard demographic questions.

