#### **Screen Failure Procedures**

Prior to entering into the study, individuals will complete a survey screener. If the individual is younger than 18 years old or does not live in Colombia, they will be deemed ineligible. Such participants will be redirected to a screen notifying them that they are ineligible for the study.

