### Sample Size and Power

Using an ANOVA model in G.Power. 3.1.9.4, we estimate that with a sample of ~8,000, alpha of 0.05, and 80% power, we can detect an effect of  $f=0.037$  for each of the primary outcomes between each arm and the control, which translates to an odds ratio of 1.14.

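### The primary models name study arm only; adjusting for education, which must be collected anyway, could make the primary differences slightly more precise if education predicts the outcomes

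*Combined protocol and SAP*

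**What the plan says.** The model for the primary outcomes is given under Sensitivity Analyses: "For all outcomes assessed between-subjects only, we will then assess whether the outcomes vary by study arm with regression models". It is logistic for dichotomous outcomes, and no covariate is named. Arms are then compared pairwise on predicted means, with a correction for multiple comparisons whose method is not stated. The same section also lists product selection among the outcomes for mixed models with product-type terms. Study Steps, however, restricts the selection task to one type of product, so each primary outcome is a single answer per person and the between-subjects model is the one that fits.

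Education appears under Hypotheses, Primary Outcomes: "We will also explore whether the impact of the nutrient warning (vs. other study conditions) on these two primary outcomes differ by" educational level. Sensitivity Analyses implements this as an interaction of label with low versus high education. Education has no role in the main contrasts.

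On timing, Study Steps says: "The study will end with standard demographic questions". The items are not listed. Age is documented only as an eligibility threshold, in Screen Failure Procedures: "If the individual is younger than 18 years old or does not live in Colombia, they will be deemed ineligible".

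Statistical Methods prescribes complete case analysis for missing data and adds: "We will use a two-sided critical alpha of 0.05 to conduct all statistical tests".

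**The concern.** In a randomised comparison, a baseline characteristic that predicts the outcome can absorb part of the residual variation and so narrow the contrasts between arms. Education is a natural candidate. The plan cannot run its interaction test without it, and a 15-20 minute survey about labels cannot plausibly change it, even though it is probably asked after exposure. Leaving it out of the main models may forgo some precision in the warning-versus-other contrasts that carry the trial's conclusions. Only precision is at stake. Neither bias nor the validity of the tests is in question.

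**Working it through.** **Inputs from the documents.** Sample Size and Power states "with a sample of ~8,000, alpha of 0.05, and 80% power", with a detectable f of 0.037 "for each of the primary outcomes between each arm and the control, which translates to an odds ratio of 1.14". Allocation is equal over four arms, so about 2,000 per arm. Tests are two-sided at 0.05.

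**Input that is assumed.** R², the share of outcome variance explained by education, is not in the documents. I use 0% to 5%, with 10% as an outer case.

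**Step 1: the plan's own figure.** A one-way ANOVA with 4 groups, N = 8,000 and noncentrality f²N gives 80% power at f = 0.0369, and 80.2% power at f = 0.037. The conversion exp(2 × 0.037 × π/√3) gives an odds ratio of 1.144. The stated figure reproduces as a four-group omnibus effect. For a single contrast of 2,000 against 2,000, 80% power needs f = 0.0443, that is, a standardised difference d = 2 × 0.0443 = 0.0886. I use that d as the 80% base below.

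**Step 2: gain on the difference scale.** The standard error is multiplied by √(1 − R²). Power is approximately Φ(z − 1.96), with z = 0.0886 / √(2(1 − R²)/2000).

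| Assumed R² | SE multiplier | Fall in SE | z | Power |
|---|---|---|---|---|
| 0% | 1.000 | 0% | 2.80 | 80.0% |
| 1% | 0.995 | 0.5% | 2.82 | 80.4% |
| 3% | 0.985 | 1.5% | 2.84 | 81.2% |
| 5% | 0.975 | 2.5% | 2.87 | 82.0% |
| 10% (outer case) | 0.949 | 5.1% | 2.95 | 84.0% |

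These figures precede any multiplicity correction.

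**Step 3: does the formula carry over to a binary outcome?** It does if the logistic fit is turned into standardised differences in predicted probabilities. In simulation (two arms of 2,000, outcome rate about 50%, two assumed covariates), the SE ratio was 0.994, 0.989, 0.975 and 0.956 at R² of about 1%, 3%, 5% and 10%. Mean adjusted and unadjusted differences agreed within 0.0001. A separate check with four arms of 2,000 and education alone gave about 1.00 at R² = 0 and about 0.97 at R² near 6%; √0.94 = 0.970.

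**Step 4: the log odds ratio.** Here the SE does not fall. At R² of about 0%, 0.5%, 2% and 7%, the adjusted-to-unadjusted SE ratio was 1.000, 1.003, 1.010 and 1.037. At 7% the estimate also moved, from 0.1327 to 0.1416, because the conditional odds ratio is a different quantity. Simulated power was 60.0% either way.

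**Step 5: missing education.** Dropping a share m of participants multiplies the SE by 1/√(1 − m): 1.005, 1.010 and 1.026 for m of 1%, 2% and 5%. Combined with Step 2, the net multiplier is √((1 − R²)/(1 − m)), so the gain vanishes once m reaches R². With an arm-blind fill it does not vanish: with 5% of one covariate missing and filled, the simulated SE ratio at R² of 5% was 0.973, and the education-only check also held at about 0.97 with 5% filled.

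**The case against.** The strongest case for leaving the plan alone has four parts.

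- **The gain is unproven and small.** The documents report no association between education and either primary outcome, so the gain may be nil, and about 2,000 per arm already keeps chance imbalance small. This stands, and it is why the point is conditional and minor.
- **Covariate adjustment does not tighten a logistic log odds ratio.** This stands for odds ratios (Step 4). It does not apply to differences in predicted probabilities, and the plan already intends to compare predicted means.
- **Demographics come last and the analysis is complete case.** Someone who answers the fruit-drink task and then breaks off has a primary outcome but no education value, and Outliers and Exclusions keeps anyone who answers at least one outcome. Adding education under the present missing-data rule could lose as much as it gains. This stands, so the fix needs its own rule for missing covariates.
- **An unadjusted analysis of a large randomised survey is a legitimate choice.** Agreed.

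A reader might also infer three stronger things that the documents do not support. One is that every primary contrast is less precise than it could be; that holds only if education is prognostic. Another is that age is available for adjustment; only an 18-or-older check is documented, and a yes/no item would be constant among those enrolled. The third is that the trial expects an effect as small as f = 0.037; the text gives this as what can be detected with about 8,000 people and states no anticipated effect.

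**Conclusion.** The point holds as an optional improvement in efficiency. The main primary models name study arm only, and education must be collected. If education predicts the outcomes, the primary differences in predicted probability carry a slightly larger standard error than necessary: about 0% to 2.5% for an assumed R² of 0% to 5%, or 0 to 2 percentage points of power from an 80% base. This rests on the assumed R², on reporting standardised differences rather than conditional odds ratios, and on not dropping people for missing education. The planned analysis is valid without the change.

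The change should not be presented as a remedy for pairwise power. At f = 0.037 (d = 0.074) a contrast of 2,000 against 2,000 has about 65% power, and adjustment raises that only to 67% at R² of 5% or 69% at 10%.

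**What to change.** 1. In Sensitivity Analyses, state that each primary logistic model contains study arm plus education, with the coding of education fixed in advance. Add age and sex only if the survey records them.
2. Report arm contrasts as standardised differences in predicted probabilities, averaged over the whole analysed sample, rather than as conditional odds ratios. The quantity estimated then stays a population-level difference.
3. In Statistical Methods, add an exception to the complete-case rule for covariates: participants with missing education are kept through a prespecified arm-blind fill, such as a missing category, so that nobody with a primary outcome is lost.
4. Keep the unadjusted percentages as the descriptive display.

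The cost is one extra missing-covariate rule and a few lines of code, with no change to data collection or sample size. Naming the covariates now also rules out a data-driven choice later.

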## INVESTIGATIONAL PLAN (brief overview)

### Study Design

The study design is a between-subjects randomized controlled trial. Qualtrics will randomly assign participants to one of four study arms in the Qualtrics survey. Participants will have an equal chance of being randomized to any of the trial arms.

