### **SCREENING AND MONITORING EVALUATIONS AND MEASUREMENTS (how measurements will be made)**

Measurements will include results from the selection and assessment tasks as well as subjective responses by participants. Secondary outcomes will include a variety of measurements, including perceived message effectiveness, 5-point Likert scale questions, and identification questions.

Question	Response Scale
Primary outcomes	
Which of these products would you rather buy?	1 = (image of control beverage) 2 = (image of experimental beverage)
Which of these products is higher in sugar?	1 = (image of control beverage) 2 = (image of experimental beverage)
Secondary outcomes	
How much does this label... 
 
make you concerned about the health consequences of consuming this product?
 
discourage you from wanting to eat consume this product?
 
make consuming this product seem unpleasant to you?
 
	1 = Very much 2 = A lot 3 = A little 4 = Very little 5 = Not at all
How likely is it for you to want to purchase this product next week, if it were available?	1 = Very much 2 = A lot 3 = A little 4 = Very little 5 = Not at all
In your opinion, which of these products is most unhealthy?	1 = (image of control beverage) 2 = (image of experimental beverage)
Do you think this product has excess [saturated fat/sugar/sodium]?	1 = Yes 0 = No
Which of these labels would discourage you most from wanting to consume this product?	[answer choices are each of the label types randomly displayed]

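### The linear mixed model for the 1–5 secondary outcomes states no robust standard error, so pairwise intervals for perceived message effectiveness and purchase likelihood can be somewhat too narrow or too wide

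*Combined protocol and SAP*

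**What the plan says.** The model is set out in the combined protocol and SAP under Sensitivity Analyses. For outcomes with several measurements per person, "we will fit mixed effects linear regression models for continuous outcomes (including PME", and the dependence within a person is handled by "treating the intercept as random to account for repeated measures". The fixed effects are arm and product, "as well as an interaction of warning message and product type". Pairwise comparisons between label types then come from the model predictions, with a correction for multiple comparisons. Nothing is said about the residual variance structure or the type of standard error.

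The measurement table gives the same response scale for the perceived message effectiveness (PME) items and for purchase likelihood: "1 = Very much 2 = A lot 3 = A little 4 = Very little 5 = Not at all". PME is named for the linear mixed model. Purchase likelihood is not, but it shares the scale and appears to be among the questions asked for yogurt, cookies and bread, so the same model is the natural reading.

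The Statistical Methods section adds: "We will use a two-sided critical alpha of 0.05 to conduct all statistical tests". The secondary hypotheses give only the direction in which means should differ. No SD, expected mean or effect size is given for either outcome.

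**The concern.** A random-intercept linear model, fitted with default options, assumes that people vary equally in every arm and that residuals vary equally in every arm and product. On a scale that stops at 1 and 5, responses bunch up as the mean nears an end, so an arm that moves the mean can also change the spread. A comparison of two arms should rest on the variances of those two arms. The default model instead gives every pair one pooled figure.

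If the warning arm were the least variable, its own intervals would be too wide and those among the other arms too narrow. If it were the most variable, the reverse would hold. Equal allocation does not remove this for pairwise contrasts, because each pair borrows variance from arms outside the pair. Neither does sample size: the ratio of model to true standard error does not depend on n. The multiplicity correction does not remove it either, since it takes the individual p-values as valid.

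**Working it through.** **The plan's own figure.** The plan states f = 0.037 "with a sample of ~8,000, alpha of 0.05, and 80% power", "which translates to an odds ratio of 1.14". A four-group F test with noncentrality 0.037² × 8,000 = 10.95 and 3 and 7,996 df has power 0.802, and exp(2 × 0.037 × π/√3) = 1.14, so the figure reproduces. It concerns the primary outcomes and carries no SD for the 1–5 scales. With "Participants will have an equal chance of being randomized to any of the trial arms", it fixes about 8,000/4 = 2,000 per arm.

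**Formulas.** With balanced data, let V be an arm's variance of the person mean over products and Vbar its average over the arms in the model.
- Model SE for any pair: √(2·Vbar/n)
- True SE for arms i and j: √((Vi + Vj)/n)
- Ratio R = √(2·Vbar/(Vi + Vj))
- Miss rate of a nominal 95% interval: 2·(1 − Φ(1.96·R))

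A mixed model fitted to simulated data gave SE 0.05579 for both pairs checked, equal to the formula, when the true SEs were 0.05223 and 0.05924.

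**Which arms are pooled.** The PME questions ask about the label and the control arm has none, so PME most naturally has three arms. Purchase likelihood has four.

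**Simple SD ratios (assumed).** Suppose the warning arm's SD is 0.8 times the others'.
- Four arms: Vbar = (3 + 0.64)/4 = 0.91. Other-versus-other R = √0.91 = 0.954, miss rate 6.2%. Warning-versus-other R = √(1.82/1.64) = 1.053, miss rate 3.9%.
- Three arms: Vbar = 2.64/3 = 0.88. R = 0.938 (6.6%) and 1.036 (4.2%).
- At 0.9 or 1.1 times, four-arm SEs are off by about 2.5% (miss rates 4.4% to 5.6%).

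**From shifts in means (assumed).** Take a latent normal response cut at ±0.4 and ±1.2 into five categories, three products and latent within-person correlation 0.5. The GDA and Nutri-Score arms lie between control and warning (one-sixth to two-fifths of the warning shift).

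| Control position | Warning shift (latent SD) | R, four arms | R, three arms |
|---|---|---|---|
| mid-scale (mean 3.0) | 0.3 | 0.996–1.004 | 0.995–1.003 |
| mid-scale | 0.5 | 0.989–1.012 | 0.988–1.008 |
| mid-scale | 1.0 | 0.957–1.049 | 0.954–1.032 |
| high (mean 3.8) | 0.5 | 0.955–1.052 | 0.962–1.030 |
| low (mean 2.0) | 0.5 | 0.962–1.042 | 0.980–1.029 |
| high (mean 3.8) | 0.9 | 0.924–1.098 | 0.923–1.047 |

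Miss rates are 4.7% to 5.3% in the first two rows, 3.9% to 6.1% in the next three, and 3.1% to 7.0% in the last.

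**Product-specific contrasts (assumed).** Here the model also pools variance over products. With cutpoints ±0.5 and ±1.5, products at −0.4, 0 and +0.4, a 0.5 SD warning shift, the other two label arms at one-third of it, and four arms:
- control mean about 3.0: R 0.986–1.036, miss rate 4.2% to 5.3%
- about 3.5: R 0.947–1.100, 3.1% to 6.3%
- about 3.9: R 0.893–1.196, 1.9% to 8.0%

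**The case against.** The strongest reply is that the defect is read from silence. The plan neither states a common variance nor rules out a robust option. That stands as far as it goes: common variance is the default reading, not a declared choice.

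A reader might infer that the error bars must be wrong whenever the arms differ as hypothesised. The documents do not support this. The hypotheses concern means only, and a moderate shift near mid-scale leaves the variances almost equal.

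A reader might also infer that the 0.05 level fails, with type I error of, say, 2.3% to 8.0%. Those values come from assumed SDs of 0.8, 1.1, 1.2 and 1.3 in four arms. If spread follows the mean, arms with different SDs also have different means, so for those pairs there is no true null and the figures describe interval miscoverage. A null pair would have equal spread and be distorted only by the other arms: with SDs of 1.2, 1.2, 1.2 and 1.0, R = √(1.33/1.44) = 0.961 and the rate is 6.0%. All these rates use an uncorrected 1.96, so none is the error rate of the planned, corrected procedure.

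Finally, the absolute effect is small. Even under the 0.8 to 1.3 set, with 2,000 per arm and one response per person, the model SE is √(2 × 1.245/2,000) = 0.0353, against a true SE of 0.0396 for the most variable pair and 0.0304 for the least: at most about 0.005 points on a 1–5 scale. That stands, and it limits the severity. It does not remove the mismatch.

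**Conclusion.** The point holds as a low-severity improvement. As written, the model's pairwise standard errors pool variance over all arms (three for PME, four for purchase likelihood) and can be too small for some pairs and too large for others. Under the assumptions above, the arm-level error is about 1% or less for moderate shifts near mid-scale. For large shifts or responses near the scale ends it is roughly 2–8% too small or up to about 10% too large, with miscoverage of about 3–7% before multiplicity correction. Product-specific contrasts may be further off.

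These sizes rest on assumed response distributions, a latent within-person correlation of 0.5 and balanced data; complete-case exclusions would change the balance slightly. They also assume that purchase likelihood uses the same model and PME only the label arms. Both primary outcomes are binary and unaffected. Nothing in the documents shows that a conclusion would change.

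**What to change.** Add to the Sensitivity Analyses section: *Standard errors for linear and mixed linear models will be robust (sandwich), clustered on participant.* Each pairwise interval then reflects the variances of the arms and product compared, whatever they are.

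The cost is one sentence and one software option. The model, point estimates and planned predicted-mean contrasts are unchanged, and with about 8,000 participants as clusters there is no material small-sample penalty. Stating it in advance also removes a later choice between types of standard error.

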conditions: nutrient warning, Nutri-Score, GDA, or a no-label control. The participants will complete a fruit-drink selection task, inquiring about healthfulness of fruit drinks with each designated front-of-package label. After completing the fruit-drink task, the participant will complete a single product assessment task. After these, the participants will answer objective understanding and perceived message effectiveness questions about a breakfast cereal. Finally, the participants will see one product with all three label types and select the most discouraging label. The study will end with standard demographic questions.

---

Subject Population	Inclusion Criteria
key criteria for Inclusion and Exclusion:	

1. 18 years old or older

2. Currently reside in Colombia

	Exclusion Criteria
	

1. Participated in previous studies linked to this study

Number Of Subjects	Approximately 8,000
Study Duration	Each subject's participation will last approximately 15-20 minutes. The entire study is expected to last 1 month.
Study Phases	

(1) Screening: screening for eligibility and obtaining consent

(2) Randomization: Randomly assigning participants to one of four conditions

(3) Survey: Direct participants to a Qualtrics survey measuring product selection and perceptions and reactions to front-of-package labels, as well as standard demographics.

Statistical Analysis Plan	We will descriptively report unadjusted means (and standard deviations) and percentages for the primary and secondary outcomes. We will use linear regression for continuous outcomes and logistic regression for dichotomous outcomes. We will conduct pairwise comparisons of the predicted means to examine differences by all label types. We will examine whether primary outcomes differ by education.
DATA AND SAFETY MONITORING PLAN	Researchers will store the study data on a remote terminal server, and only research investigators and staff will have access to the data.

---

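### Does the correction for multiple comparisons need a named family and method, set to the three nutrient-warning contrasts?

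*Combined protocol and SAP*

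**What the plan says.** The SAP's primary hypotheses are directional statements about one arm: "compared to GDA, Nutriscore, and control, a nutrient warning label will lead to" lower selection of the less healthy drink and better identification of the drink with more sugar. That makes three contrasts for each of two primary outcomes.

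The Sensitivity Analyses section, which holds the SAP's regression models, then plans "pairwise comparisons of the predicted means to examine differences by all label types. We will correct for multiple comparisons". The Protocol Synopsis gives the same comparisons without the correction: "We will conduct pairwise comparisons of the predicted means to examine differences by all label types". Statistical Methods adds: "We will use a two-sided critical alpha of 0.05 to conduct all statistical tests".

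Other comparisons also appear. The secondary hypotheses add "and all conditions compared to the control" for some secondary outcomes. Sample Size and Power describes its detectable effect as applying "for each of the primary outcomes between each arm and the control". The Study Objective asks which of the three label types discourages purchases.

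**The concern.** One sentence carries the whole multiplicity plan, and it can be read in three ways.

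1. All four arms are compared, giving six pairs. Three of these pairs answer no primary hypothesis yet share the error rate with those that do.
2. Only the labels are compared, giving three pairs. Study Steps uses the words label types without the control: "the three label types (nutrient warnings, GDA, and Nutri-Score) will be displayed underneath the product". On this reading warning versus control would drop out.
3. The correction belongs only to the repeated-measures models described just before it. The primary outcomes come from a single-product task ("We will only include selection tasks for one type of product due to survey space constraints"), so they would be tested uncorrected at 0.05. Against this, the same section lists product selection among the repeated outcomes.

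If the reading were picked after the data were seen, the evidence for the main claim could depend on that choice. At stake would be 10 to 15 points of power per contrast, or a familywise error of about 12.5% in place of 5%.

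**Working it through.** **Inputs.** About 8,000 participants, alpha 0.05 and f = 0.037 (Sample Size and Power); four arms with equal allocation (Study Design), hence 2,000 per arm. Assumptions: normal theory, and the stated effect, which the plan gives against control, applied to each warning contrast.

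**The plan's own figure.** One-way ANOVA with four groups has noncentrality N·f² = 8,000 × 0.037² = 10.95 on 3 and 7,996 degrees of freedom, which gives 80.2% power. The odds ratio is exp(2f·π/√3) = exp(0.074 × 1.814) = 1.14. Both figures reproduce, as an omnibus test. For a single contrast, z = 0.074/√(2/2,000) = 2.34, and power is 65% at an unadjusted 0.05. That shortfall exists under any choice of family and is a separate matter.

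**Which reading does the text support?** Reading 2 takes its phrase from the most-discouraging-label task, where no control can appear, and it would contradict the primary hypotheses. Reading 3 relies on a heading and on position. The section under that heading contains the SAP's only outcome models, including the simple between-subjects regressions and the education test on the primary outcomes, so the heading cannot show that the primary outcomes are excluded. The sentence on correction has no qualifier. The synopsis is a summary, and its silence contradicts nothing. A two-sided 0.05 for all tests is compatible with adjusted p-values. Reading 1, with the primary outcomes covered, is the natural one.

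**False-positive risk per outcome, all four arms equal** (1,000,000 simulated trials):

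| Procedure | Chance of any false positive |
|---|---|
| Three warning contrasts, uncorrected | 12.5% |
| Six pairs, uncorrected | 20% |
| Holm over the three warning contrasts | 4.4% to 4.5% |
| Holm over all six pairs | about 4% |
| Two separate Holm families of three, no gate | 7.8% |

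The 12.5% is the chance that at least one contrast is falsely positive. If the claim is that the warning beats all three comparators, all three tests must succeed and no adjustment is needed. Uncorrected, that happens in 0.3% of trials when all arms are equal. It happens in 5.0% in the worst case, where the warning equals one comparator and is far from the others.

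**Power per warning contrast, other arms equal, d = 0.074:**

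| Method | Three contrasts | Six pairs |
|---|---|---|
| Bonferroni | 48% | 38% |
| Holm | 55% | 41% |

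Power for all three contrasts together is 38% with Holm over three and about 19% with Holm over six. At an odds ratio of 1.30 with an assumed 50% base rate, Holm per contrast is 98% against 95%. At 1.50 there is no difference.

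**Cost of the narrower family.** Without a gate, 7.8% per outcome becomes 1 − (1 − 0.078)² = 15% over two independent primary outcomes. If the other three pairs are tested only after all three warning contrasts succeed, power for GDA or Nutri-Score versus control falls from 51% to 20%. This last figure assumes both labels lie d = 0.074 above control and the warning another 0.074 above them.

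**The case for a change.** The strongest case for a change is that the three-contrast family comes from the sponsor's own primary hypotheses, costs a few sentences, and at the planned effect doubles the chance of establishing the full claim (38% against 19%). A plan that leaves family and method open also leaves room for a choice made after the results are known.

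The power figures stand, and so does the observation that the text is brief: naming the method and family would make it clearer. Two things weaken the rest.

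First, the room for a late choice is small. A promise to correct rules out testing with no correction. Between the two Holm families, any warning contrast rejected over six pairs is also rejected over three, because its threshold in the larger family is never the more lenient one. An analyst who chose between them late could therefore not push the warning contrasts above the 5% that Holm over three already guarantees.

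Second, the three-contrast family is not the only one the documents support. The Study Objective, the pairwise plan and the sample-size text all point to an interest in every label, including each label against control. Part of the power gain comes from giving up joint error control over pairs that the investigators plan to report.

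**Conclusion.** No change to the plan follows. The SAP commits to a correction directly after the comparisons it applies to. A statistician following it would correct the pairwise comparisons on the primary outcomes as well, with sound error control: about 4% per outcome with Holm over six pairs when all arms are equal. The missing method and family are details that analysts fill sensibly.

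Choosing three contrasts over six is a trade-off: 55% against 41% power per contrast at d = 0.074, set against 7.8% rather than about 4% for any false positive per outcome without a gate, and a lower rank for the other pairs. Reasonable statisticians would differ. The difference shrinks to about 3 points at an odds ratio of 1.30 and vanishes at 1.50.

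These sizes rest on 2,000 complete responders per arm, normal theory, and the planned effect holding for each warning contrast. The odds-ratio figures also assume a 50% base rate, which the documents do not give. The conclusion would differ only if the stated correction were withheld from the primary outcomes and single contrasts were claimed separately, which the text does not say.
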